In addition, results (N=24) from an in-lab study conducted by the Cooperative Research Centre (CRC) for Alertness, Safety and Productivity with the PowerSleep device, showed positive results with SWA and executive function (verbal fluency task). An automated device based on the acoustic enhancement of slow wave sleep increased slow wave activity at the group level. In the majority of individuals, 18/24 75% (> 0% increase), 15/24 62.5% (> 5% increase). No change in cognitive outcomes was observed at the group level. At the individual level, the majority of individuals (75%) had increased slow wave activity. Magnitude of SWA increase was associated with the magnitude of improvement in executive function.

PowerSleep is a non-invasive portable light weight device designed to stimulate deep slow-wave sleep and thereby reduce daytime sleepiness associated with insufficient sleep. The concept is to stimulate deep sleep also known as Slow-Wave Sleep (SWS), to compensate for insufficient sleep duration by increasing sleep intensity. Sleep intensity can be objectively assessed by Slow-Wave Activity (SWA), defined as EEG spectral power in the frequency range 0.5-4 Hz. In normal individuals, a reduction in the amounts of SWA consistently results in reduced alertness with impaired performance due to cognitive and memory deficits.

The PowerSleep device delivers acoustic stimuli that are calibrated to stimulate SWA without awakening the user. The PowerSleep device is wearable and non-invasive, consisting of a headband with 1 integrated electrode, one mastoid reference electrode, and speakers located in the headband over each ear. The headband is adjusted via an adjustable slider. The device monitors and records EEG throughout the night, and is capable of on-line identification of sleep stages and continuous EEG analysis. EEG data collected by the PowerSleep device can be transferred to the computer by a technician after use and used to assess sleep quality. Soft audio tones (below 65dB to prevent arousals from sleep) will be administered via the speakers during deep sleep throughout the night.

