As a second test condition of this protocol, we will also utilize a different system, Phase Locked Loop (Prototype 2) to provide acoustic stimulation during sleep. This Phase locked Loop (PLL) system was developed at Northwestern University and functions similarly to the PowerSleep Prototype 1, but the stimulation will be provided using a standard PC setup at the bedside using standard polysomnography (PSG) electrodes and acoustic stimuli will be delivered through earphones at specified times during sleep to increase slow wave activity.

II. SPECIFIC AIMS/HYPOTHESES

Primary Aim:

The primary aim of this study is to assess the effects of the auditory stimulation delivered by both the PowerSleep systems (Prototype 1) and a system developed

by Northwestern University (Prototype 2) in adults with mildly sleep restricted schedules.

We hypothesize that one night of in-lab use of a PowerSleep system (Prototype 1) or Prototype 2 under an active condition (tones played to increase slow-wave activity), as compared to one night of in-lab use of the same PowerSleep system (prototype 1) or Prototype 2 under a sham condition (no tones played) will result in a significant increase ($\geq 5\%$) in cumulative or average slow-wave activity (SWA) in nonREM sleep across the whole night of sleep compared to sham. NOTE: We will also compare the relative ability of Prototype 1 versus Prototype 2 to increase the magnitude of SWA in sleep.

Secondary Aim:

The secondary aim of the study is to assess the impact of active versus sham PowerSleep Prototype 1 and Prototype 2 systems on measures of daytime function (PAL and PVT-B). The estimated effect of PowerSleep on specific measure(s) of daytime function will be used to help inform the choice of outcomes for future studies.

Exploratory endpoints:

Exploratory endpoints will include analysis of other daytime outcome assessments in relation to SWA.

III. STUDY DESIGN AND METHODS

- A. Design:** This study is a randomized, single-blind, sham-controlled pilot cross-over trial comparing the feasibility, and efficacy of 2 nights of in lab use with active versus sham conditions in adults with sleep restricted schedules. The expected duration of the study for each participant is up to 5 weeks.

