mean, standard deviation (SD), 95% confidence interval (CI) for the mean, median, minimum, and maximum; categorical variables will be summarized using the frequency count and the percentage of subjects in each category. All analyses will be conducted using either SPSS® or SAS® software.

There are no statistical criteria for terminating the study. No sensitivity analysis will be completed, and any deviations to the original statistical plan will be noted in the analysis report.

Philips Respironics will complete the data analysis on Prototype 1. In addition Philips Respironics will analyze the Prototype 2 data in the same manner.

Subject Disposition

Subject disposition, including the total number of participants enrolled, randomized, completed, early terminations and withdrawals, will be presented by treatment group, and overall. In addition, a listing will be provided with the reasons for discontinuation by treatment group.

Demographics and Baseline Characteristics

Standard subject demographics (e.g., age and gender) and baseline characteristics will be summarized for all participants enrolled and for evaluable subjects.

Treatment Compliance

It is expected that the drop-out rate will be low as the study is of short duration and will be completed in a controlled, in-lab setting.

Primary Efficacy Analysis

The primary efficacy measure for this study is the cumulative or average slow-wave activity (SWA).

The primary analysis will be done on completed participants with SWA data collected during the four conditions: Prototype 1 active and sham, Prototype 2 active and sham. A 2-way repeated measures Analysis of Variance (RMANOVA) will examine the SWA data with the repeated measures factors of therapy (active and sham) and prototype (1 and 2). An interaction factor will also be included to determine whether the active / sham effect differs between prototypes. The significance level will be $p < 0.05$.

If the required assumptions for the RMANOVA model are violated, transformation of the data or non-parametric procedures may be used.

Secondary Efficacy Analysis

The daytime outcomes will be analyzed using the same statistical model as the SWA data.

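### The primary RMANOVA specifies no active-versus-own-sham estimate for either prototype and makes no use of the 5% criterion, so it does not directly address the device-specific primary hypothesis.

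*Combined protocol and SAP*

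**What the plan says.** **Hypothesis (II. Specific Aims/Hypotheses, Primary Aim).** One active night on Prototype 1 or Prototype 2 is compared with "one night of in-lab use of the same PowerSleep system (prototype 1) or Prototype 2 under a sham condition (no tones played". The expected result is a significant increase, marked as at least 5%, in "cumulative or average slow-wave activity (SWA) in nonREM sleep across the whole night of sleep compared to sham". A note adds: "We will also compare the relative ability of Prototype 1 versus Prototype 2 to increase the magnitude of SWA in sleep".

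**Analysis (V. Statistical Analysis, Primary Efficacy Analysis).** "A 2-way repeated measures Analysis of Variance (RMANOVA) will examine the SWA data", with therapy (active, sham) and prototype (1, 2) as within-person factors and a 0.05 significance level. On the comparison of devices: "An interaction factor will also be included to determine whether the active / sham effect differs between prototypes". SWA is again described as either cumulative or average. If assumptions fail, "transformation of the data or non-parametric procedures may be used".

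**Surrounding text (V., General Considerations).** Each variable gets descriptive summaries, including a 95% CI for its mean. The sponsor is to analyse the Prototype 1 data and treat the Prototype 2 data likewise; no estimator, test or threshold is attached to that sentence. The analysis uses completers (target 10), and no sample-size calculation was made.

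**The concern.** The hypothesis is about each device against its own sham, on a percentage scale, with a 5% mark. The specified tests concern the average of the two devices and the gap between them, by default on untransformed SWA, with zero as the null value. Three things are at stake.

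- **Which device works.** A pooled effect can be carried by one device. If the interaction is not significant, a reader may credit both.
- **What 5% means.** A p-value below 0.05 does not show that 5% was reached, and an observed rise above 5% may be non-significant. The plan does not say whether 5% is a mark for the point estimate or a value that the interval must exclude.
- **What is measured.** Cumulative SWA depends on time spent in nonREM sleep as well as on intensity; average SWA does not in the same way. The two can give different answers to the 5% question.

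**Working it through.** **1. What the model tests.** Let D1 and D2 be a person's active-minus-own-sham differences for Prototypes 1 and 2. In a 2×2 within-person ANOVA, the therapy F(1, n−1) is the squared paired t for (D1+D2)/2, and the interaction F is the squared paired t for D1−D2. This identity was confirmed numerically on simulated data (n=10). Neither term is D1 or D2 alone. On the log scale, effects of +10% and 0% average to √1.10 − 1 = 4.9%, almost the same as +5% for both devices, so the therapy term cannot tell these cases apart.

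**2. Inputs.** The plan has no power figure to reproduce. From the plan: n=10 and alpha 0.05 (two-sided t, 9 df, critical value 2.262). Assumed: one device at 0% and the other at +10% (ln 1.10 = 0.0953); night-to-night SD s = 0.06/0.08/0.10 on log SWA; correlation ρ between D1 and D2 from 0 to 0.7.

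**3. Formulas.**
- Own-sham SE = s√(2/10)
- Pooled SE = s√((1+ρ)/10)
- Interaction SE = 2s√((1−ρ)/10)
- Power comes from the noncentral t. With equal SDs, the average and the difference are independent, so P(pooled significant, interaction not) = pooled power × (1 − interaction power).

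**4. Worked case, s = 0.08.**
- ρ=0: pooled 0.0477/0.0253 = 1.88, power 39%; interaction 0.0953/0.0506 = 1.88, power 39%; pattern 0.391 × 0.609 = 24%.
- ρ=0.5: pooled 0.0477/0.0310 = 1.54, power 28%; interaction 0.0953/0.0358 = 2.66, power 66%; pattern 0.280 × 0.339 = 10%.

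**5. Results for s = 6/8/10%.**

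| ρ | Pooled significant | Interaction significant | Pooled significant, interaction not |
|---|---|---|---|
| 0 | 61/39/27% | 61/39/27% | 24/24/20% |
| 0.3 | 50/32/22% | 76/52/36% | 12/15/14% |
| 0.5 | 45/28/20% | 88/66/48% | 5/10/10% |
| 0.7 | 41/25/18% | 98/86/69% | 1/3/6% |

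The working device's own-sham contrast is significant in 88/66/48% at every ρ, because its SE does not involve ρ. The ineffective device's own 95% CI lies above 0 in 2.5%. On raw SWA, simulated with ρ=0 and a between-person SD of 0.5, the last column is 24/22/17%, so the choice of scale neither causes nor cures the problem.

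**6. How 5% is read, for one device (s = 6/8/10%).**
- Lower limit above 0 needs an observed exp(2.262·s√0.2) − 1 = 6.3/8.4/10.6%.
- Lower limit above 5% needs 1.05·exp(2.262·s√0.2) − 1 = 11.6/13.9/16.2%.
- A point estimate of at least 5% when the true effect is 0: 1 − Φ(ln 1.05/(s√0.2)) = 3/9/14%.
- Chance that the lower limit exceeds 5%, from the noncentral t with ln((1+effect)/1.05)/(s√0.2): 34/21/15% at a true +10%, and 6/5/4% at a true +6.2%.

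**7. Cumulative or average (illustration only).** Take cumulative = average × nonREM time. If an average rises 6.2%, the cumulative rise is 1.062 × (1 − 0.0113) = 1.050, or 5.0%, when nonREM time is 1.1% shorter on the active night. It is 1.062 × (1 − 0.0584) = 1.000, or nil, when that time is 5.8% shorter. The Background does not say which measure its 6.2% refers to, and no document figure shows shorter nonREM time on active nights.

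**The case against.** Several points on the other side are fair.

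- **Per-prototype work is hinted at.** A reader might infer that the plan excludes any analysis by device. It does not: General Considerations says the sponsor will analyse Prototype 1 and then Prototype 2 alike. But without an estimator, test or threshold, that sentence leaves the contrast unspecified.
- **Nothing is lost from the data.** A reader might infer that the trial cannot address its hypothesis. That goes too far. The RMANOVA is already within-person, and both contrasts can be recovered from the same four nights. What is missing is pre-specification.
- **The condition means would warn a careful reader.** Partly true. Their CIs, however, include between-person spread and are not intervals for the paired effect.
- **The misreading risk may be small.** Quoting about one trial in four as the general risk would be wrong. It holds at zero correlation. If people who respond to one device tend to respond to the other, the interaction gains power and the risk falls to 1/3/6% at 0.7.
- **Transformation is already allowed.** Yes, but only if assumptions fail. The case for logs here is that the hypothesis is a percentage, not that logs gain much power.
- **It is an unpowered pilot.** This limits the harm, and the repair will rarely prove 5%. It also makes estimates with intervals the more useful output.

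**Conclusion.** The point holds as a gap in specification and should be fixed; it does not invalidate the design or the model. The planned tests address the average effect and the difference between devices, each against zero. The stated hypothesis concerns each device against its own sham, with a 5% mark.

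In the 0%/+10% scenario, the pattern that invites a wrong claim for both devices ranges from 24/24/20% down to 1/3/6% as the correlation rises from 0 to 0.7. The working device's own contrast is more sensitive than the pooled test throughout: 88/66/48% against 61/39/27% at correlation 0 and 45/28/20% at 0.5. These sizes rest on assumed SDs, correlations and true effects. The mismatch itself rests only on the text.

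That SWA is left as cumulative or average is also plain from the text. A reader might infer that the choice will reverse the result; the documents do not support that, and the figures in step 7 show only that it could.

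**What to change.** Keep the RMANOVA and its interaction, and add the following before unblinded data are seen.

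1. From paired differences in log SWA, give the active/own-sham ratio for each prototype, back-transformed to a percentage change with 95% CI.
2. For Prototype 1 versus 2, give the ratio of those ratios with 95% CI.
3. Name one primary SWA measure. Average nonREM SWA fits the stated rationale, "to compensate for insufficient sleep duration by increasing sleep intensity". Report cumulative SWA and nonREM minutes beside it, because VI. Protection for Human Participants accepts that tones may fragment sleep, and an average would not show lost nonREM time.
4. State how 5% is read: a lower limit above 0 shows an increase; a point estimate of at least 5% is only consistent with the hypothesis; only a lower limit above 5% shows that 5% was reached.
5. Draw no conclusion about a single device from the pooled effect alone.
6. State that, at n=10, the intervals will usually not settle the 5% question.

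**Cost.** Some wording and analysis work, and no extra data. Two unadjusted 95% CIs give about a 1 − 0.975² = 4.9% chance that at least one of two ineffective devices shows a lower limit above 0 (contrasts taken as independent). Turning the contrasts into Holm-adjusted confirmatory tests would be expensive: with both devices at +6.2% and uncorrelated differences, power per contrast is about 24% at night SD 8% and 15% at 10%, against 56% and 40% for the pooled log test (41% and 28% for the pooled test at correlation 0.5). Reporting them as estimates avoids that loss.

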- B. Study Participants:** We will enroll up to 60 individuals in order to complete a total of 10 participants using a cross over design. We will recruit male and female participants who satisfy the inclusion and exclusion criteria outlined in the following sections.
- C. Study-wide recruitment methods:** Potential participants will be recruited predominantly through media advertisements (ex. local newspapers, flyers, online advertisements), institutional postings, or existing online communities or site databases of patients who have previously indicated an interest in participating in research.

[name] (Principal investigator) will not be involved in recruiting or consenting research participants, or in data collection. [name] (Co-Principal Investigator) will be responsible for these aspects of the study.

- D. Setting:** Subjects will be identified from the population of prior research subjects who have agreed to be contacted for additional research experiments. New

subjects will be recruited from the general population through use of flyers/posters and online advertisements.

- E. Randomization:** An EDC will be used to control the randomization schedule. This EDC will be set-up by Philips Respironics. The Philips Prototype will be double blind, as neither the study participants, nor study staff will know which is active or sham. The Northwestern Prototype will be single-blind, however scoring will be blinded. If any Serious Adverse Events or Unanticipated Device Effects occur the study staff will alert the sponsor and the sponsor will break the blind if necessary. The study staff will alert the sponsor prior to any unblinding.

IV. INCLUSION AND EXCLUSION CRITERIA

Inclusion Criteria

- Able to provide written informed consent prior to admission
- Able to read, write and speak English
- Adult volunteers aged 21-50
- Working full time (M-F) schedule [Note: Full time is considered a 32 hour work week start time at 7am or later] or full time student
- Self-reported regular sleep schedule who are able to maintain their sleep schedule during the course of the study
- Self-reported sleep latency \leq 30 minutes
- Self-reported wake after sleep onset \leq 30 minutes
- Participants who regularly (3 of 5 work/school nights) use an alarm clock during the work/school week and who self-report:

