- Individuals who self-report a history of recurrent seizures or epilepsy or family history of hereditary epilepsy or have a history of medical conditions that could increase the chance of seizures (e.g. stroke, aneurysm, brain surgery, structural brain lesion).
- Individuals who self-report severe contact dermatitis or allergy to silver.
- Individuals who self-report moderate hearing loss.
- Inability to achieve appropriate headband fit (for prototype 1).
- Planned air travel or travel across more than one time zone during the anticipated period of the study with PowerSleep or PLL device use.
- Alpha-delta sleep on the first night in the sleep lab.
- Intentional naps during the work week.

Classes of medications that will not be allowed include:

Class	Examples
Sedating Antihistamines	chlorpheniramine, brompheniramine, diphenhydramine, doxylamine
OTC Decongestants	phenylephrine, ephedrine,

	pseudoephedrine
Sedative/Hypnotics	zolpidem, eszopiclone, zaleplon, ramelteon, triazolam, gabitril, tiagabine, suvorexant, gamma-hydroxybutyrate, tasimelteon
Anxiolytics	alprazolam, clonazepam, diazepam, lorazepam
Sedating Antidepressants	amitriptyline, nortriptyline, duloxetine, venlafaxine, mirtazapine, nefazodone, buspirone, bupropion
Medications for Attention Deficit Hyperactivity Disorder	atomoxetine, methylphenidate, amphetamine
Stimulants	amphetamine, modafinil, armodafinil
Dopamine Agonists	ropinirole, pramipexole, rotigotine
Narcotic/Opioid Analgesics	Including tramadol
Dextromethorphan	Many OTC cough products
Dietary supplements and other preparations affecting sleep-wake regulation	Kava (Piper methysticum), Ashwagandha (Withania somnifera), Valerian (Valeriana officinalis), St. Johns Wort (Hypericum Perforatum)
OTC stimulants	
Diet aids	
Melatonin	

*Participants who are on a stable and well-tolerated pharmacological treatment for hypertension, dyslipidemia, or thyroid replacement will not be excluded as long as they continue to take their medication at the same dose and at the same time(s) of day

IV. STUDY PROCEDURES AND MEASUREMENTS

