Each subject will undergo a baseline screening period with screening questionnaires, clinical history, and 1 week of actigraphy measurement to determine eligibility for inclusion in the study. Prior to the overnight study they will undergo an additional 1 week of actigraphy measurement. Each subject will have two 3 day/2 night stays, separated by one week. Including outpatient screening and the inpatient study periods, the duration of participation for each subject will be ~5 weeks. We anticipate 6 months to enroll and complete the 12 subjects. Primary data analysis should be completed within one year of starting this study.

Study Procedures:

Participants may be screened over the phone to determine eligibility. A screening script will include a general review of key inclusion and exclusion criteria, and the Stop-Bang Questionnaire to assess risk for undiagnosed obstructive sleep apnea. Participants that meet all eligibility criteria will be asked to come into the research lab for a brief daytime screening visit. Participants who are interested and eligible will be consented. Participants will be provided with information on use of the actigraph and sleep logs at

home. Participants will be asked to return their actigraph and sleep logs to the laboratory either in person or via pre-paid FedEx. Participant qualification will be assessed based on sleep logs and the actigraph results. Qualifying participants will wear the actigraph and fill out sleep logs again for the week prior to their first overnight visit.

[figure not shown]

Figure 1. Overall Study Design. Qualifying participants will be randomized to receive either stimulation or sham condition. Then each group will be further randomized to receive PowerSleep Prototype 1 or Prototype 2 system at their first overnight visit, and will receive the other condition at their second overnight visit. Overnight visits will have a one night washout in between nights. The overnight visits (Visits 3 and 4) are scheduled as two sets of 3 day/2 night overnight studies and may be completed with a washout period of 5- 14 days between visits. In order to assess sleep quality, participants with an arousal index (AI) > 20 events/hour or alpha-delta sleep during an overnight visit will be excluded from further participation in the study. On the morning following each treatment, the participants will remain the lab to complete daytime function assessments and questionnaires.

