Participants will drop off or mail their actigraph and sleep log to the Center for Circadian and Sleep Medicine for review by the study staff. The actigraph data will be reviewed by a trained technologist. Only participants that demonstrate a regular sleep schedule and an average sleep duration of 6-7 hours during the work week will be asked to return to the lab for the study. A regular sleep schedule will be defined as a bedtime between 9pm and midnight with no more than 1 hour of variability across the 7 nights. Qualifying participants will be asked to continue wearing the actiwatch and completing the sleep diary throughout the remainder of the study.

Visit 2 Procedures (3 days/2 nights with washout in between nights):

Participants will be randomly assigned to the sham or active stimulation condition during the first night of the overnight visits, and the other condition (sham or active stimulation) during the second night of the overnight visits. Participants may also be asked to undergo additional night study testing if data collected is unable to be analyzed due to unforeseen technical or environmental reasons. Participants and study staff will be blinded to the condition they are receiving during each overnight study for prototype 1. However, study staff will not be blinded during each overnight for prototype 2.

Active condition: Participants will be set-up with one of the PowerSleep Prototypes. Soft audio tones (below 65dB to prevent arousals from sleep) will be administered via the headphones during deep sleep throughout the night.

Sham condition: Participants will be set up with the same PowerSleep prototype as with the active arm, however no audio tones will be played.

Participants will typically be asked to arrive at the Sleep Disorders Center on the 7th Floor of Arkes or Galter Pavilion ~3 hours before their usual bedtime.

Upon arriving at the Sleep Disorders Center for the first overnight study, the actigraph data will be downloaded for review by a trained technologist. Only participants that demonstrate a regular sleep schedule and a sleep duration of 6-7 hours per night will be asked to remain in the study and through completion.

The PAL learning set will be completed before the participant goes to bed.

Overnight monitoring:

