The subject will be allowed to go home or to work during the day and will be instructed not to nap during the day. This will be monitored with the actigraph. The subject will return to the lab the following evening 3 hours before the usual bedtime and will be instrumented and studied as described for night 1. For example, participants that spent the night Monday and completed Tuesday morning testing will come into the lab Wednesday night for Thursday morning testing or if participants spent Tuesday night and completed Wednesday morning testing they will come into the lab Thursday night for Friday morning testing.

Visit 4 Procedures (3 days/2 nights):

Participants will return to the Sleep Disorders Center to complete the second set of overnight studies one or two weeks after the first set of overnight studies. If participants spent Monday and Wednesday night in the lab for the first set of overnight studies, they will complete the second set of overnight visits Monday and Wednesday. The actigraph data will be similarly downloaded and reviewed for further participation upon arriving at the Sleep Disorders Center. This visit will be identical to Visit 3 except that the subjects will receive the prototype system that was not used in Visit 3 (Prototype 1 or 2).

V. STATISTICAL ANALYSIS

Determination of Sample Size

Twelve participants will be enrolled in order to ensure ten completed data sets. Since this is a pilot study, no sample-size calculation was performed.

General Considerations

The primary analysis will be performed including all completed participants. Subjects who complete all 4 in lab study nights with functional devices will be included in data analysis. If the sleep data are not usable for one or more of the participants' treatment conditions, those participants will be excluded from the primary analysis, and site(s) may over-enroll to compensate for these missing data. The analysis of safety will include all randomized subjects.

All variables will be summarized by descriptive statistics. The statistics for continuous variables includes mean, median, standard deviation, minimum, maximum, 95% confidence interval (CI) for the mean, and number of observations. For categorical variables, number and percentage of subjects with the event will be presented. Continuous variables will be summarized using the number of non-missing observations,

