Provisions to Protect the Privacy Interests of Participants: Subjects will only interact with approved members of the research staff, and will have the option to decline to provide any information that they are uncomfortable revealing. Subject's medical records will only be accessed after obtaining written consent from the subject, and will only be reviewed by members of the research staff for whom review of this information is necessary for continued participation in the study (e.g. coordinator obtaining information, and study physician reviewing the information prior to admission).

Compensation for Research-Related Injury: There is no compensation available for research-related injury.

Vulnerable Populations: N/A

Community-Based Participatory Research: N/A

Sharing of Results with Participants: Study results will not be shared with the subject.

Economic Burden to Participants: There will be no cost to the subject to participate in the study.

Withdrawal Criteria:

The term "discontinuation" refers to the participant's premature withdrawal from the study prior to completing all procedures. Participants may be discontinued from the study for any of the following reasons:

- If in the investigator's judgement, continuation in the study may prove harmful to the participant. Such a decision may be precipitated by adverse events, including fever, nausea, rash, changes in vital signs, or the development of a new medical condition. The investigator will be solely responsible for making medical/safety decisions regarding the participant's continued participation in the study.
- Noncompliance.
- At the request of the participant.

The study coordinator will document whether or not each participant completed the study. If, for any participant, study treatment or assessments were discontinued, the reason will be recorded.

The study goal is to have 10 participants complete the entire study. Participants that withdrawal from the study will be replaced in order to obtain the necessary 10 completed data sets.

Early Stopping Criteria: The sponsor reserves the right to stop the study at any time.

VII. MONITORING AND QUALITY ASSURANCE

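### The primary SWA model leaves out the randomised night order, and no stated active/sham estimate per prototype matches the ≥5% hypothesis

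*Combined protocol and SAP*

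**What the plan says.** Section V, Primary Efficacy Analysis: a two-way repeated measures ANOVA "will examine the SWA data with the repeated measures factors of therapy (active and sham) and prototype (1 and 2", with their interaction, tested at p<0.05. Night, visit and sequence do not appear. General Considerations rules out sensitivity analyses. The outcome is SWA, either summed or averaged over the night, with the choice left open.

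Design. Under Visit 2 Procedures: "Participants will be randomly assigned to the sham or active stimulation condition during the first night of the overnight visits", with the other condition on the second night. The Figure 1 legend adds a second randomisation: "Then each group will be further randomized to receive PowerSleep Prototype 1 or Prototype 2 system at their first overnight visit". Of the second pair of nights, Visit 4 Procedures says: "This visit will be identical to Visit 3 except that the subjects will receive the prototype system that was not used in Visit 3". On balance, the Randomization paragraph says only "An EDC will be used to control the randomization schedule".

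First night. No adaptation night is described. The first lab night is a treatment night, and it also serves an exclusion: "Alpha-delta sleep on the first night in the sleep lab".

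Losses. Under the Figure 1 legend, participants with a high arousal index or "alpha-delta sleep during an overnight visit will be excluded from further participation in the study". Only those who complete all four nights are analysed, and under Withdrawal Criteria "Participants that withdrawal from the study will be replaced in order to obtain the necessary 10 completed data sets".

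Hypothesis. The Primary Aim expects a significant increase of at least 5% with Prototype 1 or Prototype 2, each against its own sham. The analysis section does not mention 5%, a ratio or a percentage change. It plans descriptive 95% CIs for means and says the sponsor will analyse both prototypes' data alike.

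**The concern.** Night is a factor the trial randomises, so its effect can be removed from the error at almost no cost. Left out, a difference between first and second nights adds to the spread of the active-minus-sham contrasts when orders are balanced. When they are not, it moves the estimate. With ten completers and a 5% target, a movement of a few points matters. Exclusions after an overnight visit and replacement of withdrawals can unbalance the completers even under a balanced schedule.

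The second issue is that neither planned test answers the stated hypothesis. The therapy main effect averages the two prototypes, and the interaction tests whether they differ. A significant main effect could come mostly from one prototype and leave the per-prototype question open, in a study whose declared purpose is to compare two algorithms.

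**Working it through.** The plan states that no sample-size calculation was performed, so there is no power figure to reproduce.

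**1. How a night effect enters.** Let N be night 2 minus night 1, in percentage points of SWA, and τ the active-minus-sham effect. Within a visit the contrast is τ+N if active falls on night 2 and τ−N if it falls on night 1.
- If order repeats and N recurs at both visits, the pooled contrast is τ±N. Over n completers the estimate shifts by N(n₂−n₁)/n.
- If N occurs at the first visit only, the pooled contrast is τ±N/2 and the shift is half as large.
- If order reverses and N recurs, it cancels from the pooled contrast and enters the interaction instead.

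At 7:3, (7−3)/10 = 0.4. N of 5 or 10 shifts the estimate by 2 or 4 points if recurring, and by 1 or 2 if first visit only. At 6:4 the factors are 0.2 and 0.1.

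**2. Chance of imbalance.** Binomial(10, 0.5) gives 7:3 or worse in 34.4%. If 12, 14, 16 or 20 are randomised in equal numbers and 10 complete at random, the hypergeometric probabilities are 0%, 7%, 12% and 18%.

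**3. Assumed SD.** None is given. The Background reports 18/24 individuals above 0% and 15/24 above 5%. Under normality SD = 5/(0.6745−0.3186) = 14.05 per prototype. If the two prototype contrasts are independent, the pooled SD is 14.05/√2 ≈ 10. Combining 75% above zero with the other study's mean of 6.2% gives 6.2/0.674 = 9.2, or 6.5 pooled. Sampling error in those counts allows SDs from about 6 to 54.

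**4. Illustrative power.** n=10, τ=6.2, pooled SD 10, two-sided 5%. With no night effect, 6.2/(10/√10) = 1.96 on 9 df gives 42%. With the night term at 5:5 the standard error is unchanged on 8 df, giving 41%. Without the term, N=10 raises the apparent SD to about √(100+100×10/9) = 14.5. At 5:5, with order repeating:

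| N (points) | Unadjusted, recurring | Unadjusted, first visit only | Adjusted |
|---|---|---|---|
| 0 | 42% | 42% | 41% |
| 5 | 32–33% | 39% | 41% |
| 10 | 15% | 32–33% | 41% |

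Averaged over simple randomisation, a 5-point first-visit-only effect gives about 40% unadjusted against 38% adjusted at SD 10, and 71% either way at SD 6.5.

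**5. Type I error, unadjusted, SD 10.** For a recurring 10 points it is 0.7% at 5:5 and 6.3% at 7:3. Averaged over simple randomisation it is 5.0–5.1%. The adjusted test holds about 5% throughout.

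**6. Pooled result against the per-prototype question.** Suppose one prototype gives +10%, the other 0%, and there is no night effect. The pooled test is significant in about 29% of trials (per-prototype SD 14.1) or 58% (SD 9.2). In about 70% or 42% of those, the interaction is not significant.

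**7. Which covariate.** If order is drawn separately at each visit, first-visit order removes only part of a recurring effect. At SD 10, N=10 and 5:5 at each visit, power is about 25% unadjusted, 31–32% with first-visit order, and 40–41% with the mean of the two order codes.

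**The case against.** The strongest reply is that nothing here is an error. Order is randomised, the planned test is unbiased over that randomisation, and its average type I error is nominal. A reader might infer from the missing adaptation night that the primary result is biased, or that a first-night effect is established. The documents support neither. They give no night-effect size, and under risks they say only that participants may find it hard to sleep in the laboratory, naming no night. The large gain, 15% to 41%, needs a 10-point effect that recurs at the second visit with order repeating. No section shows such a recurrence. A missing adaptation night points rather to a first-visit effect, where the gain is modest and can be a slight loss.

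The power inputs are also weak. The counts that give SD 14.05 imply a mean of 0.674×14.05 = 9.5%, not 6.2%. With that mean, power without a night effect is about 76%, not 42%. The table shows direction, not expected power.

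On the second issue, a reader might infer that no intervals and no per-prototype analysis are planned. That goes too far. Descriptive CIs for means are planned, both prototypes' data are to be analysed alike, and per-prototype effects can be read from the cell means. What remains is that no within-prototype contrast, relative scale or interval for the active/sham effect is stated.

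Finally, Figure 1 is not reproduced in the text available and may show therapy order at the second visit.

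**Conclusion.** The point stands as a cheap improvement, between worth considering and advisable, and not as a fault that invalidates the primary test. Omitting night order makes the test conservative near balance if a night effect exists. At 7:3 it moves the pooled estimate by 40% of a recurring effect or 20% of a first-visit-only effect. If there is no night effect, nothing is lost by omitting it. How much this matters depends on three things not in the text available: the night-effect size, the SD, and whether the schedule balances order and repeats it at the second visit.

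The gap between the per-prototype hypothesis of at least 5% and the planned tests does not depend on those unknowns. It is under-specification rather than a wrong model, and the undecided SWA measure belongs with it.

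**What to change.** Keep the therapy and interaction tests at p<0.05 and make these changes in the SAP.

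- Name one SWA measure and state that the analysis is on log SWA. This changes the scale and error degrees of freedom of the primary test, and the SAP should say so.
- Add night order (night 1 or 2 within visit), taken from each visit's actual therapy order in the randomisation record. If order is drawn separately at each visit, use the mean of the participant's two order codes for the pooled contrast. If order repeats or reverses for everyone, use first-visit order for the pooled contrast and first-visit order × prototype sequence for the interaction.
- State which of these designs applies, unless Figure 1 already does, and whether the EDC schedule balances night order.
- For each prototype report the order-adjusted active/sham ratio with a 95% CI, read against 1.05, as a supporting estimate with no added significance claim.

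The data are already held. The cost is one error degree of freedom per test. With no night effect at SD 10, pooled power falls from 42% to 41% at 5:5 and to 35% at 7:3, which is why a balanced schedule is worth stating. Per-prototype intervals will be wide: on 8 df about ±2.306×14.05/√10 = ±10.2 points, or ±2.306×9.2/√10 = ±6.7. They will describe the 5% question rather than settle it.
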